5.1.2.1 Other imputations

Incomplete date of initial diagnosis of cancer and date of most recent recurrence

Missing day is defaulted to the 15th of the month and missing month and day is defaulted to 01-Jan.

Incomplete assessment dates for tumor assessment

All investigation dates (e.g. MRI scan, CT scan) must be completed with day, month and year. If one or more assessment dates are incomplete but other investigation dates are available, this/these incomplete date(s) are not considered for calculation of the assessment date and assessment date is calculated as the latest of all investigation dates (e.g. MRI scan, CT scan) if the overall response at that assessment is CR/PR/SD/UNK. Otherwise – if overall response is progression – the assessment date is calculated as the earliest date of all investigation dates at that evaluation number. If all measurement dates have no day recorded, the 1st of the month is used. If the month is not completed, for any of the investigations, the respective assessment will be considered to be at the date which is exactly between previous and following assessment. If a previous and following assessment is not available, this assessment will not be used for any calculation.

Applying the cut-off to tumor assessment

For tumor related assessments, if an evaluation has some assessments done prior to cut-off date and others after the cut-off date, then the evaluation is considered post-cut-off date and will be excluded from analysis.

5.2 AEs coding/grading

Adverse events are coded using the Medical dictionary for regulatory activities (MedDRA) terminology.

Note: The latest available MedDRA version at the time of the analyses should be used. The MedDRA version used should be specified in the footnote of relevant tables.

AEs will be assessed according to the Common Terminology Criteria for Adverse Events (CTCAE) version 5.0.

The CTCAE represents a comprehensive grading system for reporting the acute and late effects of cancer treatments. CTCAE grading is by definition a 5-point scale generally corresponding to mild, moderate, severe, life threatening, and death. This grading system inherently places a value on the importance of an event, although there is not necessarily proportionality among grades (a grade 2 is not necessarily twice as bad as a grade 1).

5.3 Laboratory parameters derivations

Grade categorization of lab values will be assigned programmatically as per NCI Common Terminology Criteria for Adverse Events (CTCAE) version 5.0. The calculation of CTCAE grades will be based on the observed laboratory values only, clinical assessments will not be taken into account. The criteria to assign CTCAE grades are given in Novartis internal criteria for CTCAE grading of laboratory parameters. The latest available version of the document based on the underlying CTCAE version 5.0 at the time of analysis will be used.

For laboratory tests where grades are not defined by CTCAEv5.0, results will be graded by the low/normal/high (or other project-specific ranges, if more suitable) classifications based on laboratory normal ranges.

A severity grade of 0 will be assigned for all non-missing lab values not graded as 1 or higher. Grade 5 will not be used. For laboratory tests that are graded for both low and high values, summaries will be done separately and labelled by direction, e.g., sodium will be summarized as hyponatremia and hypernatremia.

Table 5-3 CTC grades for laboratory values in Novartis Oncology (based on CTCAE v5.0 – Nov 2017)

Lab test (toxicity)	SI unit	Lab test (NCDS)	Normal ranges (Merck manual, July 2015) and conversion factors	CTC Grades ⁽¹⁾				
				0	1	2	3	4
Hematology								
WBC ↓ WBC (Leukocytosis)	10 ⁹ /L 10 ⁹ /L	WBC WBC	3.9 – 10.7 x 10 ⁹ /L	≥ LLN	< LLN - 3.0 x 10 ⁹ /L -	< 3.0 – 2.0 x 10 ⁹ /L -	< 2.0 – 1.0 x 10 ⁹ /L > 100 x 10 ⁹ /L	< 1.0 x 10 ⁹ /L -
Hemoglobin (Anemia) Hemoglobin ↑	g/L g/L	HGB HGB	120 - 160 g/L or 7.4 - 9.9 mmol/L (F) 140 - 170 g/L or 8.7 – 10.6 mmol/L (M) (16.113 x mmol/L = g/L)	≥ LLN	< LLN - 100 g/L < LLN - 6.2 mmol/L Increase >0-20 g/L above ULN	< 100 - 80 g/L < 6.2 - 4.9 mmol/L Increase >20-40 g/L above ULN	< 80 g/L < 4.9 mmol/L Increase >40 g/L above ULN	- - -
Platelets ↓	10 ⁹ /L	PLAT	150 - 350 x 10 ⁹ /L	≥ LLN	< LLN - 75.0 x 10 ⁹ /L	< 75.0 - 50.0 x 10 ⁹ /L	< 50.0 - 25.0 x 10 ⁹ /L	< 25.0 x 10 ⁹ /L
Neutrophils ↓	10 ⁹ /L	NEUT		≥2x10 ⁹ /L	< 2.0 - 1.5 x 10 ⁹ /L	< 1.5 - 1.0 x 10 ⁹ /L	< 1.0 - 0.5 x 10 ⁹ /L	< 0.5 x 10 ⁹ /L
Lymphocytes ↓ Lymphocytes ↑	10 ⁹ /L 10 ⁹ /L	LYM LYM		≥1.5x10 ⁹ /L	< 1.5 - 0.8 x 10 ⁹ /L -	< 0.8 - 0.5 x 10 ⁹ /L > 4 - 20 x 10 ⁹ /L	< 0.5 - 0.2 x 10 ⁹ /L > 20 x 10 ⁹ /L	< 0.2 x 10 ⁹ /L -
Biochemistry								
AST ↑	U/L	AST	0 - 35 U/L or 0 – 0.58 ukat/L (60 x ukat/L = U/L)	≤ ULN	> ULN – 3.0 x ULN	> 3.0 - 5.0 x ULN	> 5.0 - 20.0 x ULN	> 20.0 x ULN
ALT ↑	U/L	ALT	0 - 35 U/L or 0 – 0.58 ukat/L (60 x ukat/L = U/L)	≤ ULN	> ULN – 3.0 x ULN	> 3.0 - 5.0 x ULN	> 5.0 - 20.0 x ULN	> 20.0 x ULN
Total bilirubin ↑	umol/L	BILI	5.1 – 20.5 umol/L or 0.3 – 1.2 mg/dL (17.1 x mg/dL = umol/L)	≤ ULN	> ULN - 1.5 x ULN	> 1.5 - 3.0 x ULN	> 3.0 - 10.0 x ULN	> 10.0 x ULN
Alk. Phosphatase ↑	U/L	ALP	36 - 92 U/L or 0.5 - 1.5 ukat/L (60 x ukat/L = U/L)	≤ ULN	> ULN - 2.5 x ULN	> 2.5 - 5.0 x ULN	> 5.0 - 20.0 x ULN	> 20.0 x ULN
Creatinine ↑	umol/L	CREAT	61.9 - 115 umol/L or 0.7 – 1.3 mg/dL (88.4 x mg/dL = umol/L)	≤ ULN	> ULN - 1.5 x ULN	> 1.5 - 3.0 x ULN	> 3.0 - 6.0 x ULN	> 6.0 x ULN
Creatinine kinase ↑	U/L	CK	30 - 170 U/L or 0.5 – 2.83 ukat/L (60 x ukat/L = U/L)	≤ ULN	> ULN - 2.5 x ULN	> 2.5 - 5.0 x ULN	> 5.0 - 10.0 x ULN	> 10.0 x ULN
Albumin (Hypoalbuminemia)	g/L	ALB	35 - 55 g/L or 3.5 to 5.5 g/dL	≥ LLN	< LLN - 30 g/L	< 30 - 20 g/L	< 20 g/L	-
Total Cholesterol ↑	mmol/L	CHOL	3.88 – 5.15 mmol/L or 150 - 199 mg/dL (38.67 x mg/dL = mmol/L)	≤ ULN	> ULN - 7.75 mmol/L > ULN - 300 mg/dL	> 7.75 -10.34 mmol/L > 300 – 400 mg/dL	>10.34-12.92 mmol/L > 400 – 500 mg/dL	>12.92 mmol/L > 500 mg/dL
Lipase ↑	U/L	LIPASE	<95 U/L or <1.58 ukat/L (60 x ukat/L = U/L)	≤ ULN	> ULN - 1.5 x ULN	> 1.5 - 2.0 x ULN	> 2.0 - 5.0 x ULN	> 5.0 x ULN
Amylase ↑	U/L	AMYLASE	0 - 130 U/L or 0 – 2.17 ukat/L (60 x ukat/L = U/L)	≤ ULN	> ULN - 1.5 x ULN	> 1.5 - 2.0 x ULN	> 2.0 - 5.0 x ULN	> 5.0 x ULN
Uric acid (Hyperuricemia)	umol/L	URATE	150 - 470 umol/L or 2.5 – 8 mg/dL (59.48 x mg/dL = umol/L)	Defined by clinical criteria only in CTCAE V5				

ULN = Upper Limit of Normal range; LLN = Lower Limit of Normal range

				CTC Grades ⁽¹⁾				
Lab test (toxicity)	SI unit	Lab test (NCDS)	Normal ranges (Merck manual, July 2015) and conversion factors	0	1	2	3	4
Phosphorus (Hypophosphatemia)	mmol/L	PHOS	0.97 – 1.45 mmol/L or 3.0 - 4.5 mg/dL (0.32 x mg/dL = mmol/L)	Defined by clinical criteria only in CTCAE V5				
Calcium (corrected) (Hypercalcemia)	mmol/L	CACALC	2.2 - 2.6 mmol/L or 9 - 10.5 mg/dL (0.2495 x mg/dL = mmol/L)	≤ ULN	> ULN - 11.5 mg/dL > ULN - 2.9 mmol/L	> 11.5 - 12.5 mg/dL > 2.9 - 3.1 mmol/L	> 12.5 - 13.5 mg/dL > 3.1 - 3.4 mmol/L	> 13.5 mg/dL > 3.4 mmol/L
Calcium (corrected) (Hypocalcemia)	mmol/L	CACALC		≥ LLN	< LLN - 8.0 mg/dL < LLN - 2.0 mmol/L	< 8.0 - 7.0 mg/dL < 2.0 - 1.75 mmol/L	< 7.0 - 6.0 mg/dL < 1.75 - 1.5 mmol/L	< 6.0 mg/dL < 1.5 mmol/L
Magnesium (Hypemagnesemia)	mmol/L	MG	0.62 – 0.99 mmol/L or 1.5 – 2.4 mg/dL (0.4114 x mg/dL = mmol/L)	≤ ULN	> ULN - 3.0 mg/dL > ULN - 1.23 mmol/L	-	> 3.0 - 8.0 mg/dL > 1.23 - 3.3 mmol/L	> 8.0 mg/dL > 3.3 mmol/L
Magnesium (Hypomagnesemia)	mmol/L	MG		≥ LLN	< LLN - 1.2 mg/dL < LLN - 0.5 mmol/L	< 1.2 - 0.9 mg/dL < 0.5 - 0.4 mmol/L	< 0.9 - 0.7 mg/dL < 0.4 - 0.3 mmol/L	< 0.7 mg/dL < 0.3 mmol/L
Glucose (non-fasting) (Hyperglycemia)	mmol/L	GLUCSN	<7.8 mmol/L or <140 mg/dL (0.05551 x mg/dL = mmol/L)	Defined by clinical criteria only in CTCAE V5				
Glucose (fasting) (Hyperglycemia)	mmol/L	GLUCSF	3.9 – 5.8 mmol/L or 70 - 105 mg/dL (0.05551 x mg/dL = mmol/L)					
Glucose (Hypoglycemia)	mmol/L	GLUCSN/ GLUCSF		≥ LLN	< LLN - 55 mg/dL < LLN - 3.0 mmol/L	< 55 - 40 mg/dL < 3.0 - 2.2 mmol/L	< 40 - 30 mg/dL < 2.2 - 1.7 mmol/L	< 30 mg/dL < 1.7 mmol/L
Potassium (Hyperkalemia)	mmol/L	K	3.5 - 5.0 mmol/L (0.2558 x mg/dL = mEq/L = mmol/L)	≤ ULN	> ULN - 5.5 mmol/L	> 5.5 - 6.0 mmol/L	> 6.0 - 7.0 mmol/L	> 7.0 mmol/L
Potassium (Hypokalemia)	mmol/L	K		≥ LLN	< LLN - 3.0 mmol/L	-	< 3.0 - 2.5 mmol/L	< 2.5 mmol/L
Sodium (Hypernatremia)	mmol/L	SODIUM	136 - 145 mmol/L (0.435 x mg/dL = mEq/L = mmol/L)	≤ ULN	> ULN - 150 mmol/L	> 150 - 155 mmol/L	> 155 - 160 mmol/L	> 160 mmol/L
Sodium (Hyponatremia)	mmol/L	SODIUM		≥ LLN	< LLN - 130 mmol/L	< 129 - 125 mmol/L	< 124 - 120 mmol/L	< 120 mmol/L
Triglyceride ↑	mmol/L	TRIG	< 2.82 mmol/L or < 250 mg/dL (0.01129 x mg/dL = umol/L)	< 150 < 1.71	≥ 150 - 300 mg/dL ≥ 1.71 – 3.42 mmol/L	> 300 - 500 mg/dL > 3.42 – 5.7 mmol/L	> 500 - 1000 mg/dL > 5.7 – 11.4 mmol/L	> 1000 mg/dL > 11.4 mmol/L
Coagulation								
INR↑	1	INR	0.8 – 1.2	≤ 1.2	> 1.2- 1.5	> 1.5- 2.5	> 2.5	-
Activated partial thromboplastin time ↑	sec	APTT	25 - 35 sec	≤ ULN	> ULN - 1.5 x ULN	> 1.5 - 2.5 x ULN	> 2.5 x ULN	-
Fibrinogen ↓	g/L	FIBRINO	1.5 – 3.5 g/L or 150 – 350 mg/dL (0.01 x mg/dL = g/L)	≥ LLN	< LLN - 0.75 x LLN	< 0.75 - 0.5 x LLN	< 0.5 - 0.25 x LLN	< 0.25 x LLN

ULN = Upper Limit of Normal range; LLN = Lower Limit of Normal range

(1) LAB CTC grades 1, 2, 3, 4 overrule the study specific (central or local) normal range criteria, e.g. if ULN of Sodium is 151 mmol/L and the value is 151 mmol/L, CTC grade 2 is assigned although the value is ≥ ULN.

Clinical criteria such as 'asymptomatic' or 'Life-threatening consequences' are not considered for determination of LAB CTC grades. Concomitant usage of therapy is also not considered.

Values and LNRs for blood differentials can be given as %, absolute values should then be calculated using WBC. Generally, ≥ 1.5 x 10⁹/L (lymphocytes) and ≥ 2 x 10⁹/L (neutrophils) are considered as LAB CTC grade 0

The comparison with baseline is not considered for derivation of LAB CTC grades

Imputation Rules

CTC grading for blood differentials is based on absolute values. However, this data may not be reported as absolute counts but rather as percentage of WBC.

If laboratory values are provided as '<X' (i.e. below limit of detection) or '>X', prior to conversion of laboratory values to SI unit, these numeric values are set to X.

The following rules will be applied to derive the WBC differential counts when only percentages are available for a xxx differential

$$\text{xxx count} = (\text{WBC count}) * (\text{xxx \%value} / 100)$$

Further derivation of laboratory parameters might be required for CTCAE grading. For instance, corrected calcium can be derived using the reported total calcium value and albumin at the same assessment using the following formula:

$$\text{Corrected Calcium (mg/dL)} = \text{Calcium (mg/dL)} - 0.8 [\text{Albumin (g/dL)} - 4]$$

In order to apply the above formula, albumin values in g/L will be converted to g/dL by multiplying by 0.1, calcium values in mmol/L will be converted to mg/dL by dividing by 0.2495. For calculation of laboratory CTC grades 0 and 1, the normal range for derived corrected calcium is set to the same limits (in mg/dL) as for calcium.

CTC grades for the derived absolute WBC differential counts (neutrophils, lymphocytes) and corrected calcium will be assigned as described above for grading.

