Recently, several studies have demonstrated the meaningful activity of platinum-based chemotherapy for TNBC Isakoff et al 2015; Tutt et al 2014. In the multicenter phase II clinical trial of single agent platinum in metastatic TNBC Isakoff et al 2015, 86 subjects received first-or second-line cisplatin (75 mg/m2) or carboplatin (AUC 6) by physician's choice once every 3 weeks. The overall response rate (ORR) was 25.6%, including three complete responses and 19 partial responses. The ORR was 29% in first line, and 12% in second line mTNBC Isakoff et al 2015. The larger TNT study Tutt et al 2014, a randomized phase III trial, compared carboplatin with docetaxel, both as single agents, in 376 subjects with mTNBC or *BRCA1/2* breast cancer. Using carboplatin in first line TNBC yielded an ORR of 31%; the PFS was 3.1 months (95% CI: 2.5-4.2 months). The study showed no evidence of superior response to carboplatin compared to docetaxel in unselected TNBC subjects, with lower incidence of AE with carboplatin Tutt et al 2014.

Bone marrow suppression is the dose-limiting toxicity of carboplatin. The most frequent AEs in a cohort of patients with ovarian cancer receiving single-agent carboplatin as second line treatment were myelotoxicity (thrombocytopenia, neutropenia, anemia), and nausea and vomiting. Carboplatin has limited nephrotoxic and ototoxic potential; peripheral neurotoxicity is infrequent (US label Paraplatin®). In the TBCRC009 trial, single-agent carboplatin had generally mild toxicity in mTNBC, with fatigue, nausea, electrolyte abnormalities, and hematologic toxicity among the most common adverse events: Thrombocytopenia occurred in 49% of subjects, anemia in 65%, neutropenia in 35%, hypomagnesemia in 23%, and anorexia in 9%. Grade 3 and 4 adverse events were rare. Grade 3 and 4 adverse events occurring in at least 5% of all subjects included fatigue, neutropenia, dyspnea, anemia, hyperglycemia, and hyponatremia Isakoff et al 2015.

Carboplatin is administered as infusion therapy. The major route of elimination of carboplatin is renal excretion. A mathematical formula incorporating the glomerular filtration rate (GFR) and carboplatin target area under the concentration versus time curve (AUC in mg/mL•min) is commonly used to determine the initial dose, since it allows compensation for subject variations in pretreatment renal function.

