All deaths (on-treatment, up to 150 days after last administration of LAG525/spartalizumab or up to 30 days after the last dose of carboplatin whichever comes last, and post-treatment) will be summarized.

All AEs, deaths and serious adverse events (including those from the pre and post-treatment periods) will be listed and those collected during the pre-treatment and post-treatment period will be flagged.

Vital signs

Data on vital signs will be tabulated based on notable vital sign values. All vital signs data will be listed by treatment group, participant and visit/time, notable values will be flagged.

12-lead ECG

12-lead ECGs including PR, QRS, QT and QTcF will be obtained for each participant during the study. ECG data will be read and interpreted centrally.

All ECG data will be listed by treatment group, participant and visit/time, abnormalities will be flagged. Categorical analysis of QT/QTc interval data based on the number of participants meeting or exceeding predefined limits in terms of absolute QT/QTc intervals or changes from baseline will be presented.

Clinical laboratory evaluations

All laboratory data will be listed by treatment group, participant, and visit/time.

Grading of laboratory values will be assigned programmatically as per NCI Common Terminology Criteria for Adverse Events (CTCAE) version 5.0. The calculation of CTCAE grades will be based on the observed laboratory values only, clinical assessments will not be taken into account.

CTCAE Grade 0 will be assigned for all non-missing values not graded as 1 or higher. Grade 5 will not be used.

For laboratory tests where grades are not defined by CTCAE version 5.0, results will be categorized as low/normal/high based on laboratory normal ranges.

The following listings/summaries will be generated separately for hematology and biochemistry tests:

• Listing of all laboratory data with values flagged to show the corresponding CTCAE version 5.0 grades if applicable and the classifications relative to the laboratory normal ranges

For laboratory tests where grades are defined by CTCAE version 5.0

- Worst post-baseline CTCAE grade (regardless of the baseline status). Each participant will be counted only once for the worst grade observed post-baseline.
- Shift tables using CTCAE version 5.0 grades to compare baseline to the worst ontreatment value

For laboratory tests where grades are not defined by CTCAE version 5.0,

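### The hyponatremia grade limits printed in SAP Table 5-3 do not meet, so sodium of 129 to <130 and 124 to <125 mmol/L has no grade and falls to Grade 0 by default

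*SAP*

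**What the plan says.** SAP 5.3 assigns laboratory grades by program, under CTCAE version 5.0, from the observed value alone. It names a sponsor-internal criteria document as the source, to be used in its latest version at the time of analysis, and prints Table 5-3.

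The hyponatremia row of that table reads:

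- Grade 0: at or above the lower limit of normal (LLN)
- Grade 1: "< LLN - 130 mmol/L"
- Grade 2: "< 129 - 125 mmol/L"
- Grade 3: "< 124 - 120 mmol/L"
- Grade 4: below 120 mmol/L

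The default for anything left over is in SAP 5.3: "A severity grade of 0 will be assigned for all non-missing lab values not graded as 1 or higher". Protocol 12.5.2 has the same rule: "CTCAE Grade 0 will be assigned for all non-missing values not graded as 1 or higher".

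Under SAP 2.9.3 the grades feed the worst post-baseline grade table, the baseline-to-worst shift tables and the listing of Grade 3 or 4 laboratory toxicities.

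In the total cholesterol row, Table 5-3 gives the unit conversion as "38.67 x mg/dL = mmol/L".

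**The concern.** Grade 1 stops at 130 and Grade 2 starts below 129. Grade 2 stops at 125 and Grade 3 starts below 124. Each break leaves an interval 1 mmol/L wide with no grade, and the default sends it to Grade 0. Reporting sodium in whole numbers does not help, because 129 and 124 are themselves whole numbers.

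At stake is how low sodium is described in the safety tables. Sodium is a scheduled chemistry test (Protocol Table 8-5), and changes in chemistry values are part of the secondary safety endpoint. Hyponatremia is also a plausible finding with this treatment. Protocol 1.1.3.4, describing a trial of single-agent platinum, lists "dyspnea, anemia, hyperglycemia, and hyponatremia" among the Grade 3 and 4 adverse events that reached at least 5% of subjects, while also saying that Grade 3 and 4 events were rare.

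**Working it through.** **Is the less-than sign strict?** The notes under Table 5-3 say that "≥ 2 x 10⁹/L (neutrophils) are considered as LAB CTC grade 0", while the Grade 1 neutrophil band runs from below 2.0 to 1.5. A value of exactly 2.0 is therefore outside Grade 1, so the number after the sign is excluded. The lymphocyte row works the same way at 1.5. A text-extraction fault is unlikely, since the ≤ and ≥ signs survive in the same table.

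**The plan's own example.** Footnote 1 to Table 5-3 gives the only worked sodium grade: a value of 151 with an upper limit of 151 mmol/L is Grade 2. The hypernatremia row defines Grade 2 as above 150 up to 155. Since 150 < 151 ≤ 155, the literal reading reproduces Grade 2.

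**Hyponatremia row, same literal reading.** Inputs: the four printed bands, the table's LLN of 136 mmol/L, first limit excluded, second limit included, then the Grade 0 default. The last column closes the gaps by setting Grade 2 to 125 ≤ Na < 130 and Grade 3 to 120 ≤ Na < 125.

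| Sodium (mmol/L) | Band met as printed | After default | Contiguous limits |
|---|---|---|---|
| 136 and above | 0 | 0 | 0 |
| 130–135 | 1 | 1 | 1 |
| 129 | none | 0 | 2 |
| 125–128 | 2 | 2 | 2 |
| 124 | none | 0 | 3 |
| 120–123 | 3 | 3 | 3 |
| below 120 | 4 | 4 | 4 |

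As sodium falls from 130 to 129 to 128, the grade goes 1, 0, 2. From 125 to 124 to 123 it goes 2, 0, 3. In steps of 0.1 mmol/L, the ungraded values are 129.0–129.9 and 124.0–124.9. With contiguous limits no value is ungraded.

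**Is this the table's general style?** The numeric limits of 26 graded rows or row pairs in Table 5-3 were compared. Hyponatremia is the only one whose adjacent grades do not meet (130 against 129, and 125 against 124).

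**Effect on a subject.** The worst-grade table counts each subject once. If the lowest sodium is 124 and another post-baseline value is 126, the subject is shown as Grade 2 instead of Grade 3. The subject falls to Grade 0 only if no other post-baseline value earns a grade.

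**Cholesterol factor.** The row's normal range is 150–199 mg/dL or 3.88–5.15 mmol/L. Dividing gives 150/38.67 = 3.88 and 199/38.67 = 5.15, which match. Multiplying as printed, 200 mg/dL becomes 200 × 38.67 = 7734 mmol/L, whereas 200/38.67 = 5.17 mmol/L.

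**The case against.** The strongest reply is that Table 5-3 may not be what is programmed. SAP 5.3 points to the latest internal criteria document, which is not among the documents. If its limits meet and the programs follow it, the fault stays on the page. This stands. A reader might infer that Grade 2 and Grade 3 results are certain to be lost; the documents support that only if the table is coded as printed.

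The Grade 0 outcome is also open to dispute, because the row reserves Grade 0 for values at or above the LLN, which 129 and 124 fail. That is fair, but it means the default and the table contradict each other, which is part of the defect.

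Nor would the results vanish. SAP 2.9.3 lists all laboratory data with their class against the normal range, so a sodium of 124 would still appear there as low. Clinically significant abnormalities are recorded and graded separately as adverse events (Protocol 8.4.1 and 10.1.1). Only the programmed laboratory grade is at risk.

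A reader might also take one whole-number value in five in each of the ranges 125–129 and 120–124 to mean that 20% of such events are lost. That figure is per result and assumes an even spread for which the documents give no data; it does not carry over to subjects.

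Finally, these grades are descriptive. The study decision rests on response rate, and the SAP Introduction says that the amended plan has no inferential analysis. This limits the importance of the point but does not remove the error.

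**Conclusion.** The point holds for the SAP as printed. Two intervals of sodium, 129 to <130 and 124 to <125 mmol/L, have no grade, and the default makes them Grade 0 against the row's own definition. If the printed limits are programmed, every result in these intervals is under-graded, and a sodium of 124 is absent from the Grade 3/4 laboratory listing. A subject's worst grade changes only when no other post-baseline value grades as high.

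The number of results or subjects affected cannot be estimated from the documents. That 129 belongs in Grade 2 and 124 in Grade 3 is inferred from the table's own pattern; the CTCAE text was not available to confirm it. Response analyses and investigator-graded adverse events are not affected.

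The inverted cholesterol factor is clerical. The grade limits in that row are printed in both units, so grading does not need the factor.

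**What to change.** In the hyponatremia row of SAP Table 5-3, make the limits meet as they do in the other rows: Grade 2 from below 130 to 125 mmol/L and Grade 3 from below 125 to 120 mmol/L, with Grades 1 and 4 unchanged. Replacing the strict sign with ≤ at 129 and 124 would repair whole-number results only; it would leave 129.1–129.9 and 124.1–124.9 ungraded.

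Confirm the new limits against CTCAE v5.0 and the internal criteria document named in SAP 5.3, and check which limits the grading programs use. Rerun the sodium grading and its tables and listing only if the programs used the printed limits.

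As a minor erratum, print the cholesterol conversion as mg/dL divided by 38.67.

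The cost is two cut-points and one conversion factor in the SAP, a check of the code, and at most a rerun of the sodium outputs.

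### SAP Table 5-3 leaves sodium of 129 to <130 and 124 to <125 mmol/L in no hyponatremia grade, so the Grade 0 default, applied as printed, under-grades those values

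*SAP*

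**What the plan says.** The hyponatremia row of SAP Table 5-3 (Section 5.3) gives Grade 0 as at or above the lower limit of normal (LLN; the printed normal range starts at 136 mmol/L), Grade 1 as "< LLN - 130 mmol/L", Grade 2 as "< 129 - 125 mmol/L", Grade 3 as "< 124 - 120 mmol/L", and Grade 4 as below 120 mmol/L.

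SAP Section 5.3 adds a catch-all: "A severity grade of 0 will be assigned for all non-missing lab values not graded as 1 or higher". Protocol Section 12.5.2 has the same rule: "CTCAE Grade 0 will be assigned for all non-missing values not graded as 1 or higher".

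On the source of the limits, SAP Section 5.3 states: "Grade categorization of lab values will be assigned programmatically as per NCI Common Terminology Criteria for Adverse Events (CTCAE) version 5.0". It continues: "The criteria to assign CTCAE grades are given in Novartis internal criteria for CTCAE grading of laboratory parameters", and then: "The latest available version of the document based on the underlying CTCAE version 5.0 at the time of analysis will be used". That internal document is not part of the supplied material.

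SAP Section 2.9.3 uses the grades in three places: the worst post-baseline grade per participant, shift tables from baseline to worst on-treatment value, and a listing of all Grade 3 or 4 laboratory toxicities.

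**The concern.** Grade bands for a laboratory value should cover the whole abnormal range, with each band starting where the milder one ends. Here Grade 1 ends at 130 but Grade 2 starts below 129, and Grade 2 ends at 125 but Grade 3 starts below 124. That leaves two gaps, each 1 mmol/L wide.

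The catch-all makes the gaps matter. Without it, a value in a gap would have no grade and would probably prompt a query. With it, a program that follows the printed table silently records an abnormal sodium as Grade 0, below the grade of milder values just above it. The table's footnote that Grades 1 to 4 overrule the laboratory's normal range does not help, because no such grade has been assigned to these values.

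At stake is the reporting of hyponatremia in the laboratory safety tables. The SAP's introduction says it was amended ahead of the final close-out report for safety and PK, so these tables are among its main outputs.

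**Working it through.** **Inputs.** The five cells of the hyponatremia row, LLN = 136 mmol/L (Table 5-3; a laboratory's own LLN may differ), and the Grade 0 catch-all.

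**Reading rule.** The number after the inequality sign is excluded and the number after the dash is included. Rows with shared limits need this reading, since otherwise a value on a limit would fall in two grades. It also agrees with the one sodium grade that the SAP works out itself: a footnote says that 151 mmol/L with an upper limit of 151 is Grade 2, and the hypernatremia band above 150 up to 155 gives Grade 2.

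**Applied to the row, for sodium Na in mmol/L:**

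| Sodium | Printed band met | Grade as printed | Grade if limits meet |
|---|---|---|---|
| Na ≥ 136 | Grade 0 cell | 0 | 0 |
| 130 ≤ Na < 136 | Grade 1 | 1 | 1 |
| 129 ≤ Na < 130 | none | 0 (catch-all) | 2 |
| 125 ≤ Na < 129 | Grade 2 | 2 | 2 |
| 124 ≤ Na < 125 | none | 0 (catch-all) | 3 |
| 120 ≤ Na < 124 | Grade 3 | 3 | 3 |
| Na < 120 | Grade 4 | 4 | 4 |

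A scan from 115.0 to 139.9 in steps of 0.1 finds ungraded values only at 129.0–129.9 and 124.0–124.9. With limits that meet, it finds none.

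**Order of severity.** In whole numbers, 130, 129, 128 score 1, 0, 2, and 125, 124, 123 score 2, 0, 3. The grade should not fall as sodium falls, but here it does so twice.

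**Comparison with the rest of the table.** I checked successive limits in 29 graded scales of Table 5-3, taking AST with ALT and lipase with amylase as one scale each. Hyponatremia is the only one whose limits do not meet. The hypernatremia row directly above it is continuous at 150, 155 and 160.

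**Effect on one participant.**
- Worst sodium 129 to <130: should be Grade 2. As printed, the worst grade is 1 if another value lies in 130 to <LLN, and otherwise 0.
- Worst sodium 124 to <125: should be Grade 3. As printed, the worst grade is 2 if another value lies in 125 to <129; failing that, 1 if another value lies in 130 to <LLN; otherwise 0. In every case the participant is missing from the Grade 3/4 listing for sodium.

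**The case against.** **The program may not use these cells.** This is the strongest point. SAP Section 5.3 names CTCAE v5.0 and the latest internal grading document as the source of the criteria, so Table 5-3 may be only a printed copy with a slip in it. This stands: the documents do not show that any output is wrong. It does not clear the table, which would then contradict its own source.

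**The intended grades are clear.** Dropping the inequality sign and reading whole-number bands of 129–125 and 124–120 covers every integer. That reading still leaves 129.5 and 124.5 ungraded. SAP Section 2.9.3 pools central and local laboratories, and Table 5-3 prints a mg/dL conversion for sodium, so non-integer values cannot be excluded.

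**The Grade 0 cell disagrees with the catch-all.** The row's own Grade 0 cell requires a value at or above LLN, which 129 and 124 do not meet when LLN is 136. A careful programmer might raise a query. But the catch-all is explicit and appears in both documents.

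**The consequence is limited.** This stands. These are descriptive summaries, and no efficacy endpoint or decision rule is touched. Adverse event tables use the grade recorded for the event (Protocol Section 10.1.1, SAP Section 2.9.1), not Table 5-3. The protocol's background figures on hyponatremia, such as 1 of 356 participants with a related Grade 3 or 4 event on LAG525 plus spartalizumab (Section 1.1.3.3.2), are adverse event reports and say nothing about how often a sodium result would fall in a gap. All laboratory data are also listed against the normal range, so the value itself stays visible.

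**Conclusion.** The table is wrong as written. Sodium of 129 to <130 and 124 to <125 mmol/L has no hyponatremia grade, and the stated default turns it into Grade 0. Under that literal reading, a participant whose worst sodium falls in either gap is under-graded in the worst-grade and shift tables, and one whose lowest sodium is 124 to <125 drops out of the Grade 3/4 listing.

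A reader might infer three stronger things that the documents do not support.
- *That Grade 2 and Grade 3 hyponatremia disappear from the safety tables.* They do not: 125 to <129 is still Grade 2 and 120 to <124 is still Grade 3.
- *That a known share of Grade 3 cases is lost.* One of the five whole numbers from 120 to 124 is affected. If lowest values were spread evenly over those five, the share would be 1/5 = 20%. If each lower value were 0.9, 0.8 or 0.7 times as frequent as the one above, it would be 24%, 30% or 36%. These are assumed distributions. With no sodium data in the documents, neither the share nor the number of participants can be computed.
- *That the reported outputs are already wrong.* That holds only if the grading program uses the printed limits, which cannot be seen from here.

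**What to change.** In the hyponatremia row of SAP Table 5-3, write Grade 2 as `< 130 - 125 mmol/L` and Grade 3 as `< 125 - 120 mmol/L`. These limits follow from the row's own Grade 1 floor of 130 and Grade 2 floor of 125, and they make the bands meet as in the other scales checked.

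Check both limits against the internal grading criteria that SAP Section 5.3 names and against the grading program. If the program used the printed limits, re-run the sodium worst-grade table, the shift table and the Grade 3/4 listing. If it did not, correcting the table is enough.

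The cost is two table cells and one check of the program, plus a re-run of the sodium outputs only if the check shows that it is needed.
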